8. Current or history of significant alcohol consumption for a period of more than 3 consecutive months within 1 year prior to screening (significant alcohol consumption is defined as more than 20 g/day in females and more than 30 g/day in males, on average).

Commercially Confidential Information

10. Clinical evidence of hepatic decompensation or severe liver impairment as defined by the presence of any of the following abnormalities:

- Serum albumin < 32 g/L
- INR > 1.3
- Direct bilirubin > 13 mg/L
- ALT or AST > 8× ULN
- Alkaline Phosphatase > 3 × ULN
- History of esophageal varices, ascites or hepatic encephalopathy
- Splenomegaly

Commercially Confidential Information

12. Presence of cirrhosis on liver biopsy or clinical diagnosis of cirrhosis.

Commercially Confidential Information

16. Patients taking medications prohibited by the protocol. See [Section 5.2](#) for further details.

17. For those patients that have had a previous liver biopsy: Significant weight loss (>15%) or change in clinical status (in the opinion of the investigator) since the diagnostic liver biopsy to screening (refer to [Section 4.1 #3](#)).

Commercially Confidential Information

22. History of non-alcohol drug abuse within the 12 months prior to dosing, or evidence of such abuse as indicated by the laboratory assays conducted during screening and baseline.

23. Women of child-bearing potential, defined as all women physiologically capable of becoming pregnant, **unless** they are using basic methods of contraception during dosing and for 5 days (approximately 5 times the terminal half life) after stopping study medication. **Basic contraception methods include:**

- Total abstinence (when this is in line with the preferred and usual lifestyle of the subject. Periodic abstinence (e.g., calendar, ovulation, symptothermal, post-ovulation methods) and withdrawal are not acceptable methods of contraception
- Female sterilization (have had surgical bilateral oophorectomy with or without hysterectomy) or tubal ligation at least six weeks before taking study treatment. In case of oophorectomy alone, only when the reproductive status of the woman has been confirmed by follow up hormone level assessment
- Male sterilization (at least 6 months prior to screening). For female subjects on the study the vasectomized male partner should be the sole partner for that subject
- Barrier methods of contraception: Condom or Occlusive cap.

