- Use of oral (estrogen and progesterone), injected or implanted combined hormonal methods of contraception or placement of an intrauterine device (IUD) or intrauterine system (IUS), or other forms of hormonal contraception that have comparable efficacy (failure rate <1%), for example hormone vaginal ring or transdermal hormone contraception. In case of use of oral contraception women should have been stable on the same pill for a minimum of 3 months before taking study treatment.

Women are considered post-menopausal and not of child bearing potential if they have had 12 months of natural (spontaneous) amenorrhea with an appropriate clinical profile (e.g. age appropriate, history of vasomotor symptoms) or have had surgical bilateral oophorectomy (with or without hysterectomy), total hysterectomy or tubal ligation at least six weeks ago. In the case of oophorectomy alone, only when the reproductive status of the woman has been confirmed by follow up hormone level assessment is she considered not of child bearing potential.

Commercially Confidential Information

Commercially Confidential Information

The investigator must ensure that all patients being considered for the study meet the above eligibility criteria.

Patient selection is to be established by checking through all eligibility criteria at screening and baseline. A relevant record (e.g. checklist) of the eligibility criteria must be stored with the source documentation at the study site.

Provided patients meet all other eligibility criteria, patients with a single lab value outside of the allowable range may be considered eligible for enrolment, as long as the abnormal lab value is within 10% of the allowable value. Platelets and eGFR values must always fall inside the allowable range as listed in the inclusion and exclusion criteria.

No additional exclusions may be applied by the investigator, in order to ensure that the study population will be representative of all eligible patients.

5 Restrictions for Study Subjects

For the duration of the study, the subjects should be informed and reminded of the restrictions outlined in this section.

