7.2 Discontinuation of study treatment

Discontinuation of study treatment for a patient occurs when study treatment is stopped earlier than the protocol planned duration. Discontinuation of study treatment can be decided by either the subject or the investigator.

Study treatment must be discontinued under the following circumstances:

- Patient decision - patients may choose to discontinue study treatment for any reason at any time.
- The investigator believes that continuation would negatively impact the safety of the patient or the risk/benefit ratio of trial participation.
- Any protocol deviation that results in a significant risk to the patient's safety
- Pregnancy (see [Section 8.6](#) (Safety) and [Section 9.6](#) (Pregnancy reporting))
- Discontinuation may be considered when patients have to be treated by prohibited medications on a case by case basis.

- Use of prohibited treatment as per recommendations in [Table 5-1](#)
- Hypersensitivity (CTCAE grade 2 or higher) reaction to LIK066 requiring intervention.
- Clinically significant diarrhea, suspected to be related to the study drug and not responsive to recommended management per SOM that may put the patient at risk (identified by investigator after consultation with the sponsor)
- Symptomatic orthostasis confirmed by repeated orthostatic blood pressure changes (more than a 20 mmHg drop in systolic or 10 mmHg drop in diastolic blood pressure and increase in heart rate >20 bpm (compared to sitting results) when blood pressure and pulse are taken after at least 3 minutes (standing)
- Clinically significant urinary tract or genitourinary infections, at the discretion of the investigator and consultation with the sponsor
- Clinically symptomatic hypoglycemia confirmed by repeated blood glucose levels (<56 mg/dL)
- Ketoacidosis (symptoms of ketoacidosis include nausea, vomiting, abdominal pain, unusual tiredness and trouble breathing) confirmed by blood pH and ketones.
- For ALT, AST, total bilirubin and/or alkaline phosphatase elevations mandating study treatment discontinuations, please refer to [Section 9.3](#) and [Table 9-1](#) and [Table 9-2](#) for further instructions and monitoring. Of note, ALT and AST are abnormal at baseline in this study. Thus only elevation to >2X of the baseline value will trigger events listed in [Section 9.3](#).
- Adverse events, abnormal laboratory values or abnormal test result that indicate a safety risk to the patient, in the opinion of the investigator

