9.3 Liver safety monitoring

To ensure patient safety and enhance reliability in determining the hepatotoxic potential of an investigational drug, a standardized process for identification, monitoring and evaluation of liver events has to be followed. The following two categories of laboratory abnormalities and AEs have to be considered during the course of the study 1) Liver laboratory triggers which will require repeated assessments of the abnormal laboratory parameter and 2) Liver events which will require close observation, follow up monitoring, and the completion of the standard base liver eCRF pages.

Please refer to [Table 9-1](#) for complete definitions of liver events.

Table 9-1 Liver Event Definitions

	Definition/ threshold
Liver laboratory triggers	
 ALT or AST $\geq 2 \times$ baseline value $1.5 \times \text{ULN} < \text{TBL} < 2 \times \text{ULN}$
Liver events	
 ALT or AST $> 5 \times \text{ULN}$ ALP $> 2 \times \text{ULN}$ (in the absence of known bone pathology) TBL $> 2 \times \text{ULN}$ (in the absence of known Gilbert syndrome) ALT or AST $> 3 \times \text{ULN}$ and INR $> 1.5 \text{ ULN}$ Potential Hy's Law cases (defined as ALT or AST $> 3 \times \text{ULN}$ and TBL $> 2 \times \text{ULN}$ [mainly conjugated fraction] without notable increase in ALP to $> 2 \times \text{ULN}$) Any clinical event of jaundice (or equivalent term) ALT or AST $> 3 \times \text{ULN}$ accompanied by (general) malaise, fatigue, abdominal pain, nausea, or vomiting, or rash with eosinophilia Any adverse event potentially indicative of a liver toxicity*

*These events cover the following: hepatic failure, fibrosis and cirrhosis, and other liver damage-related conditions; the non-infectious hepatitis; the benign, malignant and unspecified liver neoplasms

TBL: total bilirubin; ULN: upper limit of normal

Follow-up of liver events

Every liver event defined in [Table 9-1](#) should be followed up by the investigator or designated personnel at the trial site, as summarized below. Additional details on actions required in case of liver events are outlined in [Table 9-2](#).

For liver laboratory triggers

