- Repeating liver chemistry tests (ALT, AST, TBL, PT/INR, ALP and GGT) to confirm elevation within the next 7 days. If any of the lab tests described in [Table 9-1](#) are abnormal, all tests should be repeated. These liver chemistry repeats should preferentially be performed using the central laboratory, with the results provided via the standard electronic transfer. If results will not be available from the central laboratory within 24 hours, then the repeats can also be performed at a local laboratory to monitor the safety of the patient. If a liver event is subsequently reported, any local liver chemistry tests previously conducted that are associated with this event should have results reported on the unscheduled local laboratory CRF.
- If the initial elevation is confirmed, close observation of the patient will be initiated, including consideration of treatment interruption if deemed appropriate.

For Liver Events

- Discontinuation of the investigational drug (refer to [Section 7.2](#) (Discontinuation of study treatment), if appropriate)
- Hospitalization of the patient if appropriate
- Causality assessment of the liver event

Thorough follow-up of the liver event should include:

- Repeating liver chemistry tests to confirm elevation as appropriate. Testing should include PT/INR ALT, AST, ALP, and GGT. If total bilirubin is elevated > 2 x ULN, fractionation into direct and indirect bilirubin is required. To rule out muscular origin of transaminase elevations, CPK should be measured along with liver chemistry tests. Frequency of retesting should be done once a week if abnormalities stabilize or the study drug has been discontinued and the subject is asymptomatic. Retesting should be continued up to resolution or stabilization as described above.
- Obtaining a more detailed history of symptoms and prior or concurrent diseases.
- Obtaining a history of concomitant drug use (including nonprescription medications and herbal and dietary supplement preparations), alcohol use, recreational drug use, and special diets.
- Exclusion of underlying liver disease, as specified in [Table 9-3](#).
- Imaging such as abdominal US, CT or MRI, as deemed appropriate by the investigator
- Obtaining a history of exposure to environmental chemical agents.
- Considering gastroenterology or hepatology consultation.

All follow-up information, and the procedures performed must be recorded as appropriate in the CRF.

Table 9-2 Actions required for Liver Events

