Criteria	Actions required	Follow-up monitoring
Potential Hy's Law case ^a	
 • Discontinue the study drug immediately • Hospitalize, if clinically appropriate • Establish causality • Complete liver CRF 	ALT, AST, TBL, Alb, PT/INR, ALP and GGT until resolution ^c (frequency at investigator discretion)
ALT or AST		
> 10 × ULN	
 • Repeat within 48 hr • If elevation persists, discontinue drug • Hospitalize if clinically appropriate • Establish causality • Complete liver CRF 	ALT, AST, TBL, Alb, PT/INR, ALP and GGT until resolution ^c (frequency at investigator discretion)

Criteria	Actions required	Follow-up monitoring
> 3 × ULN AND INR > 1.5	
 Discontinue the study drug immediately Hospitalize, if clinically appropriate Establish causality Complete liver CRF 	ALT, AST, TBL, Alb, PT/INR, ALP and GGT until resolution ^c (frequency at investigator discretion)
> 5 to ≤ 10 × ULN	
 Repeat LFT within 1 week If elevation persists continue follow up, If elevation persists for more than 3 weeks discontinue drug Establish causality Complete liver CRF 	ALT, AST, TBL, Alb, PT/INR, ALP and GGT until resolution ^c (frequency at investigator discretion)
> 3 × ULN AND accompanied by symptoms ^b	
 Discontinue the study drug immediately Hospitalize if clinically appropriate Establish causality Complete liver CRF 	ALT, AST, TBL, Alb, PT/INR, ALP and GGT until resolution ^c (frequency at investigator discretion)
> 3 to ≤ 5 × ULN if normal baseline or >2 × baseline if elevated before drug exposure (patient is asymptomatic)	
 Repeat LFT within 1 week If elevation is confirmed, initiate close observation of the subject 	Investigator discretion Monitor LFT within 1 to 4 weeks
ALP (isolated)		
> 2 × ULN if normal baseline (in the absence of known bone pathology)	
 Repeat LFT within 48 hours If elevation persists, establish causality Complete liver CRF 	Investigator discretion Monitor LFT within 1 to 4 weeks or at next visit
TBL (isolated)		

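### Section 7.2 ties the liver events to a rise above 2 × baseline, but the ALT/AST stopping limits in Section 9.3 use multiples of ULN only; for some eligible patients the two give different actions

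*Protocol*

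**What the plan says.** Protocol Section 7.2 lists the circumstances in which study treatment must be discontinued. For liver enzymes it sends the reader to Section 9.3 and Tables 9-1 and 9-2. It notes that ALT and AST are abnormal at baseline in this trial, and concludes: "Thus only elevation to >2X of the baseline value will trigger events listed in" Section 9.3.

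Section 9.3 does not repeat that condition.

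- **Table 9-1** makes ALT or AST above 5 × ULN a liver event at any baseline. A doubling of baseline appears only in the lower tier, as a laboratory trigger for repeat testing.
- **Table 9-2** has five ALT/AST rows plus a potential Hy's Law row. Above 10 × ULN, the drug stops if the repeat within 48 hours confirms it. Above 5 and up to 10 × ULN: "If elevation persists for more than 3 weeks discontinue drug". The row "> 3 × ULN AND accompanied by symptoms" requires an immediate stop, as do the row above 3 × ULN with INR above 1.5 and the Hy's Law row. None of these refers to baseline.
- The one ALT/AST row that does ("if normal baseline or >2 × baseline if elevated before drug exposure (patient is asymptomatic") leads only to repeat testing and close observation.

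For liver events, the text of Section 9.3 points back to Section 7.2: "Discontinuation of the investigational drug (refer to" Section 7.2, if appropriate.

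On eligibility, Section 4.2 excludes "ALT or AST > 8× ULN". A single laboratory value outside its range may be accepted "as long as the abnormal lab value is within 10% of the allowable value".

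**The concern.** Patients must have raised ALT to enter, so a limit in multiples of ULN and a limit in multiples of baseline can separate widely. Two examples show that each reading has a cost.

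- **Tables govern.** A patient enters at 8 × ULN and improves to 6 × ULN. The tables record a liver event and require the drug to stop if the value stays above 5 × ULN for more than 3 weeks. Section 7.2 records nothing, because 6 is far below 16.
- **Section 7.2 governs.** A patient rises from 6 to 11.5 × ULN. Twice baseline is 12, so Section 7.2 records no event. Table 9-2 stops the drug if a repeat confirms the value.

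The first reading takes some patients off drug although their ALT has not worsened, and ALT at Week 12 is the primary variable (Section 11.4.1). The second delays stopping in a trial whose own risk section (3.6) lists hepatic toxicity.

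**Working it through.** The documents give no figure to reproduce here. The check is threshold arithmetic.

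**Inputs**

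- b = baseline ALT or AST in multiples of ULN. Highest eligible value: 8 (Section 4.2, criterion 10), or 8 × 1.10 = 8.8 with the 10% allowance.
- Section 7.2 limit: 2b.
- Table limits L: 3 (with symptoms, INR above 1.5, or bilirubin above 2 × ULN), 5 (isolated event) and 10 (confirmed on repeat).

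**Formula.** An on-treatment value x meets the table but not Section 7.2 when L < x ≤ 2b. That range is non-empty only if b > L/2:

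- L = 3: b > 1.5
- L = 5: b > 2.5
- L = 10: b > 5

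**Ranges of x (× ULN) where the texts differ**

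| b | 2b | 3 × ULN rows | 5 × ULN event | 10 × ULN row |
|---|---|---|---|---|
| 2 | 4 | 3 to 4 | none | none |
| 2.5 | 5 | 3 to 5 | none | none |
| 3 | 6 | 3 to 6 | 5 to 6 | none |
| 4 | 8 | 3 to 8 | 5 to 8 | none |
| 5 | 10 | 3 to 10 | 5 to 10 | none |
| 6 | 12 | 3 to 12 | 5 to 12 | 10 to 12 |
| 8 | 16 | 3 to 16 | 5 to 16 | 10 to 16 |
| 8.8 | 17.6 | 3 to 17.6 | 5 to 17.6 | 10 to 17.6 |

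Lower ends are exclusive and upper ends inclusive.

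**Unchanged values.** A patient with b > 5 already exceeds 5 × ULN, so the event is met with no change in ALT. A patient with b > 3 already exceeds 3 × ULN, so new nausea, fatigue or abdominal pain alone activates the immediate stop. For b between 2.5 and 5, the 5 × ULN conflict needs a real rise. At b = 3 the value must lie above 5 and up to 6 × ULN, and stay above 5 for more than 3 weeks before the drug stops.

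**Timing of the 3-week stop.** Suppose persistence is counted from the Day 7 sample (an assumption). Then 7 + 21 = Day 28 is exactly 3 weeks, and the row requires more. A stop comes after Day 28 and costs at most 84 − 28 = 56 of 84 treatment days. If the decision waits for the next chemistry visible in Table 8-1, on Day 56, it costs 84 − 56 = 28 days. Unscheduled repeats could place it between the two. Section 7.2 costs 0 days in the same patient.

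**The case against.** **Section 7.2 can be read as a study-specific condition laid over generic tables.** It gives its reason, cites the tables, and Section 9.3 refers back to it with room for judgement. This is the best defence, and it probably describes the intent for isolated enzyme rises. It does not settle the matter. Applied literally, it would also switch off the Hy's Law, INR and 10 × ULN stops for anyone at or below 2 × baseline, which is hard to believe was meant. Table 9-2 is also headed as required actions and omits the condition.

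**Redaction.** Confidential text follows the list in Section 7.2, and some exclusion criteria are hidden. The statement that no order of precedence is given therefore applies to the visible text only. A hidden, tighter ALT/AST entry limit is unlikely, because it would make the visible 8 × ULN limit redundant.

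**Safeguards.** Section 7.2 also requires stopping for abnormal laboratory values that the investigator judges a safety risk. Bilirubin above 2 × ULN (with normal baseline) and jaundice have their own rows. The sponsor monitors unblinded throughout. These limit the harm under the Section 7.2 reading, but do not tell a site which rule applies.

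**Stronger readings.** A reader might infer that every patient with baseline above 2.5 × ULN gets opposite instructions. The documents do not support that: the on-treatment value must lie between the table limit and 2b, and the 5-to-10 row also needs more than 3 weeks' persistence. A reader might also infer that the primary comparison is biased. That cannot be assessed. The model, missing-data handling and sensitivity analyses (Protocol 11.4.2 to 11.4.4) are redacted, and Section 7.2 asks patients who stop drug to return for assessments where possible.

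**Conclusion.** The rule is wrong as written, and the point is of moderate importance. In the visible text, Section 7.2 and the ALT/AST stopping rows of Section 9.3 give different actions for on-treatment values above the table limit and not above 2b. This starts at b > 1.5 for the 3 × ULN rows, b > 2.5 for the isolated 5 × ULN event and b > 5 for the 10 × ULN stop. Patients entering above 5 × ULN meet a liver event with no change in ALT.

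The conclusion rests on the visible entry limit of 8 × ULN (8.8 with the allowance) and on no redacted sentence settling which text governs. The number of patients is unknown, because the documents give neither the ULN nor the distribution of baseline ALT and AST. Any head count, or any fixed number of treatment days lost, would be an assumption. The point concerns ALT and AST only; the isolated bilirubin stop does carry a baseline condition.

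**What to change.** Replace the Section 7.2 sentence that limits the events to values above 2 × baseline, and put one rule into Section 7.2, Table 9-1 and Table 9-2:

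- The isolated 5 × ULN event, and the 3 × ULN row with symptoms, apply only if the value is also above 2 × baseline.
- Potential Hy's Law, above 3 × ULN with INR above 1.5, and confirmed above 10 × ULN apply at any baseline.

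The isolated asymptomatic limit then becomes min(10, max(5, 2b)): 5 × ULN for b ≤ 2.5, 6 for b = 3, 8 for b = 4, and 10 for b ≥ 5. An unchanged ALT alone never stops the drug, since entry is at most 8.8 × ULN. A confirmed value above 10 × ULN always does.

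The cost is one sentence and the matching table rows, in an amendment or clarification letter, with no new visits or tests. Two downsides should be stated openly. Patients entering at 2.5 to 5 × ULN may rise up to two-fold before an isolated ALT/AST event, as Section 7.2 already intends. Patients entering above 5 × ULN stop before doubling: just above a 25% confirmed rise from 8 × ULN (10/8 = 1.25), or about 14% from 8.8 × ULN (10/8.8 ≈ 1.14). That departs from Section 7.2 for this group, in exchange for a fixed ceiling.

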> 2 × ULN if normal baseline (in the absence of known Gilbert syndrome)	
 Repeat LFT within 48 hours If elevation persists, discontinue the study drug immediately Hospitalize if clinically appropriate Establish causality Complete liver CRF 	ALT, AST, TBL, Alb, PT/INR, ALP and GGT until resolution ^c (frequency at investigator discretion) Test for hemolysis (e.g., reticulocytes, haptoglobin, unconjugated [indirect] bilirubin)
> 1.5 to ≤ 2 × ULN (patient is asymptomatic)	
 Repeat LFT within the next week If elevation from baseline is confirmed, initiate close observation of the patient 	Investigator discretion Monitor LFT within 1 to 4 weeks or at next visit

Criteria	Actions required	Follow-up monitoring
Jaundice	
 Discontinue the study drug immediately Hospitalize the patient Establish causality Complete liver CRF 	ALT, AST, TBL, Alb, PT/INR, ALP and GGT until resolution ^c (frequency at investigator discretion)
Any AE potentially indicative of a liver toxicity*	
 Consider study drug interruption or discontinuation Hospitalization if clinically appropriate Establish causality Complete liver CRF 	Investigator discretion

*These events cover the following: hepatic failure, fibrosis and cirrhosis, and other liver damage-related conditions; the non-infectious hepatitis; the benign, malignant and unspecified liver neoplasms

^aElevated ALT/AST > 3 × ULN and TBL > 2 × ULN but without notable increase in ALP to > 2 × ULN

^b(General) malaise, fatigue, abdominal pain, nausea, or vomiting, or rash with eosinophilia

^cResolution is defined as an outcome of one of the following: (1) return to baseline values, (2) stable values at three subsequent monitoring visits at least 2 weeks apart, (3) remain at elevated level after a maximum of 6 months, (4) liver transplantation, and (5) death.

Table 9-3 Exclusion of underlying liver disease

Disease	Assessment
Hepatitis A, B, C, E	
 IgM anti-HAV; HBSAg, IgM anti-HBc, HBV DNA; anti-HCV, HCV RNA, IgM & IgG anti-HEV, HEV RNA
CMV, HSV, EBV infection	
 IgM & IgG anti-CMV, IgM & IgG anti-HSV; IgM & IgG anti-EBV
Autoimmune hepatitis	
 ANA & ASMA titers, total IgM, IgG, IgE, IgA
Alcoholic hepatitis	
 Ethanol history, gGT, MCV, CD-transferrin

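### Entry admits ALP up to 3 × ULN, but Table 9-1 makes ALP above 2 × ULN a liver event whatever the baseline, and Table 9-2 has no ALP row for a raised baseline

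*Protocol*

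**What the plan says.** Five places in the Protocol bear on alkaline phosphatase (ALP).

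- **Section 4.2, exclusion criterion 10** lists "Alkaline Phosphatase > 3 × ULN" among the findings that exclude a patient, so a value at or below 3 × ULN passes. The closing text of Section 4.2 allows a patient with one laboratory value out of range to be considered, "as long as the abnormal lab value is within 10% of the allowable value". That allowance is withheld for platelets and eGFR, but not for ALP.
- **Table 9-1 (Section 9.3)** lists ALP above 2 × ULN as a liver event. Its only qualifier is "in the absence of known bone pathology".
- **Table 9-2, row for isolated ALP**, is limited to "> 2 × ULN if normal baseline (in the absence of known bone pathology").
- **The potential Hy's Law definition** carries the same ALP condition in Table 9-1 and in footnote a of Table 9-2. The footnote reads "but without notable increase in ALP to > 2 × ULN". Neither place gives a baseline value or a multiple of baseline.
- **Section 7.2** sends ALT, AST, bilirubin and ALP elevations to Section 9.3 and adds: "Of note, ALT and AST are abnormal at baseline in this study". From this it concludes that only a rise to more than twice baseline triggers the Section 9.3 events. ALP is not named in that note.

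**The concern.** These rules apply to the same analyte in the same patient but use different reference points: a fixed multiple of ULN at entry, a lower fixed multiple in the event definition, and a normal baseline in the action table. Some patients whom the entry criterion accepts already meet the event definition.

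The main cost is inconsistent handling. Section 9.3 sets out to standardise how liver events are identified and followed. For these patients an unchanged entry value sets off the full liver-event follow-up, while the table that should say what to do about ALP is silent. An event recorded this way reflects the patient's state at entry, not an effect of treatment.

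The secondary stake is the potential Hy's Law category. Its row in Table 9-2 requires study drug to be stopped at once. Whether a patient with raised entry ALP can reach that row depends on how the ALP condition is read, and two sites could read it differently. Section 3.6 names hepatic toxicity as a risk of the drug, so the wording should leave no doubt.

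**Working it through.** The plan has no figure to reproduce here. The check compares ranges and then follows two example patients through the rules. The example values are illustrative.

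**Step 1. Range allowed at entry.** Criterion 10 passes ALP ≤ 3.0 × ULN. With the single-value tolerance, 3.0 × 1.10 = 3.3, so ALP ≤ 3.3 × ULN may be accepted.

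**Step 2. Range that is a liver event.** Table 9-1: ALP > 2.0 × ULN, without known bone pathology.

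**Step 3. Overlap.** ALP > 2.0 and ≤ 3.0 × ULN (≤ 3.3 with the tolerance) is both eligible on this criterion and a liver event.

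**Step 4. A patient stable at ALP 2.5 × ULN, no known bone pathology.**

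| Rule | Condition | Result |
|---|---|---|
| Criterion 10 | excluded above 3 × ULN | 2.5 < 3, eligible |
| Table 9-1, ALP line | above 2 × ULN | 2.5 > 2, liver event, with change from baseline 0 |
| Section 9.3, general follow-up | every Table 9-1 liver event | applies |
| Table 9-2, ALP row | baseline must be normal | baseline raised, row does not apply |
| Section 7.2 baseline note | names ALT and AST | does not name ALP |

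The asymmetry with the transaminases is visible inside Table 9-2. The asymptomatic ALT/AST row has one branch for a normal baseline and another, more than 2 × baseline, for a raised one. The ALP row has only the first branch, although criterion 10 admits raised ALP.

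**Step 5. The Hy's Law condition.** Keep ALP at 2.5 × ULN. Let ALT go from 2.5 to 4 × ULN and total bilirubin (TBL) exceed 2 × ULN, with no symptoms, no jaundice and INR not above 1.5.

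- *Read as a rise:* 2.5 − 2.5 = 0, so there is no increase. The patient is a potential Hy's Law case and the immediate-stop row applies.
- *Read as a level:* 2.5 > 2, so the patient is not a potential Hy's Law case.

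On the level reading, the remaining rows are:

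- ALT 3 to 5 × ULN or raised baseline: the raised-baseline branch needs more than 2 × 2.5 = 5 × ULN. Here 4 / 2.5 = 1.6 times baseline, so it is not met.
- TBL above 2 × ULN: headed as isolated and limited to a normal bilirubin baseline. Its first step is a repeat within 48 hours, with drug stopped if the elevation persists.
- Had ALT been higher, the row for above 5 and up to 10 × ULN starts with a repeat within 1 week, and the row above 10 × ULN with a repeat within 48 hours.

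Three further Table 9-2 rows require an immediate stop and carry no ALP condition: ALT or AST above 3 × ULN with INR above 1.5; ALT or AST above 3 × ULN with the listed symptoms; and jaundice. The Hy's Law ambiguity therefore changes the required action only when none of these three applies.

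**The case against.** The strongest reply is that little goes wrong in practice.

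**The Hy's Law wording speaks of an increase.** A patient who enters at 2.5 × ULN and stays there has had none, so remains a potential Hy's Law case. This reading is at least as natural as the level reading. A reader might infer that patients with ALP above 2 × ULN at entry can never be classed as potential Hy's Law cases. The text does not support that; it only fails to exclude it.

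**Such patients stay under liver monitoring.** TBL above 2 × ULN is a liver event in its own right. The INR, symptom and jaundice rows still require an immediate stop. The general liver-event steps and Section 7.2 leave the investigator free to stop treatment on a safety concern. All of this stands, and it confines the secondary point to an asymptomatic patient without jaundice and with INR at or below 1.5.

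**A missing ALP row does not mean no instructions.** The general follow-up in Section 9.3 covers every Table 9-1 event, and the ALP row itself does not call for stopping drug. For a stable, isolated ALP the visible effect is extra work-up and reporting. This also stands.

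**The Section 7.2 note could be stretched to ALP**, since its bullet lists ALP among the analytes. But the note gives only the abnormal baseline of ALT and AST as its reason, and neither table repeats it for ALP.

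**The group is small.** Primary biliary cholangitis, primary sclerosing cholangitis and known bile duct obstruction are excluded, known bone pathology is carved out, and the tolerance up to 3.3 × ULN is discretionary. Redacted exclusion criteria may narrow the range further. This limits the size of the problem but does not remove the conflict between the rules.

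**Conclusion.** The inconsistency holds. Followed as written, the Protocol accepts patients with ALP above 2 and up to 3 × ULN (up to 3.3 with the tolerance), defines them as liver events without any change in their value, and gives them no ALP row in the action table. This is a conflict between stated rules, not missing detail.

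The Hy's Law point is secondary and conditional. An immediate stop is lost only if the ALP condition is read as a level, ALT or AST exceeds 3 × ULN with TBL above 2 × ULN, and symptoms, jaundice and INR above 1.5 are all absent.

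The number of patients affected cannot be estimated and may be zero. A reader might attach a percentage to the roughly 110 planned patients, but the documents give no baseline ALP distribution. Such a figure would in any case count raised entry ALP, not changed handling, which is at most a subset. A reader might also infer that reported Hy's Law counts would be distorted; no visible analysis in Protocol Section 11.5.2 or SAP Section 7.2 tabulates such cases.

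The conclusion assumes that no redacted criterion sets a tighter ALP limit at entry.

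**What to change.** The sponsor should reconcile four items: exclusion criterion 10, the ALP line of Table 9-1, the ALP row of Table 9-2, and the potential Hy's Law definition in both Table 9-1 and footnote a. Each should say, consistently, whether the ALP condition is a level or a change from the patient's own baseline. The action table should then be checked so that every ALP value that counts as an event under Table 9-1 has a matching row. If the Section 7.2 baseline note is meant to reach ALP, it should say so. Which threshold and which action apply is for the sponsor's hepatic safety experts.

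The cost is wording in Sections 4.2, 7.2 and 9.3, made through a protocol amendment. No test, visit or patient is added.
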